#### **8.2.5     *Unscheduled Visits***

Unscheduled visits may be performed at any time, at the Investigator's discretion. Patients who come in for an unscheduled visit should bring their study medication and patient diary.

### **8.3     *Study Termination***

If the Sponsor or their designee, the Investigator, or the Medical Monitor discovers conditions arising during the study that indicate the study should be halted, the study may be terminated. Conduct of the study may also be terminated at a particular study site while the study continues at other sites. Conditions that may warrant termination include, but are not limited to:

- The discovery of an unexpected, significant, or unacceptable risk to the patients enrolled in the study;
- Failure of the Investigator to enter patients at an acceptable rate;
- Insufficient adherence to protocol requirements; or
- A decision on the part of the Sponsor to suspend or discontinue development of the study medication.

## **9. DATA HANDLING AND RECORD KEEPING**

### **9.1 Data Quality Assurance**

The Sponsor (or Sponsor's designee) will conduct a site visit to verify the qualifications of each Investigator, inspect the site facilities, and inform the Investigator of his or her responsibilities and the procedures for ensuring adequate and correct documentation.

A training extensive site initiation visit will be held to introduce Investigators and their personnel to the study protocol, EDC, procedures, and regulatory requirements.

The Investigator is required to prepare and maintain adequate and accurate case histories designed to record all observations and other data pertinent to the study for each study participant. All information recorded in the EDC for this study must be consistent with the patient's source documentation (e.g., medical records).

During the course of the study, a monitor will make site visits to review protocol compliance, compare EDC with individual patients' medical records, assess study medication accountability, and ensure that the study is being conducted according to pertinent regulatory requirements. Entries in the EDC will be verified against source documents. The review of medical records will be performed in a manner that ensures patient confidentiality is maintained.

Regulatory authorities of certain countries, the IRB/IEC, and/or the Sponsor's or designee's Clinical Quality Assurance Group may perform source data checks and/or on-site audit inspections. Investigators and their institutions will provide direct access to source data and documents to these authorities. The Investigator assures the Sponsor and their designee of the necessary support at all times.

### **9.2 Case Report Forms and Source Documentation**

Electronic Data Capture (EDC) and patient diary will be used in this study. The Sponsor or designee will provide a password to each staff member who has the authorization to implement the EDC.

The electronic data for each patient will be checked against source documents at the study site by the site monitor. Any information recorded directly into the EDC (i.e., information for which there is no prior written or electronic record) will be considered source data. The patient diary will be considered source data. A copy of the patient diary and the EDC with audit trail and final data of the EDC including data management changes will be placed in the Investigator's study file.

A Screening Log will be maintained, listing all patients screened, including patients who do not qualify for enrollment.

Instances of missing data will be discussed with the Investigator for resolution. If necessary, data query forms will be generated and sent to the site for further clarifications or corrections. The Sponsor or designee will perform a quality control review on the database. If a self evident correction document is generated during the study, the document must be approved and signed by each principal investigator.

### **9.3 Archiving Study Records**

Essential documents should be retained for a minimum of 25 years after the last approval of a marketing application in an ICH region, and until there are no pending or contemplated marketing applications in an ICH region or at least 25 years have elapsed since the formal discontinuation of clinical development of the investigational product. However, these documents should be retained for a longer period if required by the applicable laws. The Sponsor or designee must be notified in writing if the Investigator moves or if the storage location of documents is changed.

## 10. STATISTICAL METHODS

### 10.1 General Statistical Methods

All data collected in the database will be presented in the data listings.

Continuous data will be summarized by treatment group using descriptive statistics (n, mean, standard deviation, standard error of the mean, median, minimum, and maximum). Categorical data will be tabulated by treatment group and category.

In order for the requirements of the combination rule to be satisfied, both comparisons of the combination to the components alone must show the combination to be statistically significantly better than the component alone using a two-sided 0.05 significance level.

Unless otherwise noted, all analyses and summaries will be based on the microbiological intent-to-treat (MITT), the pathogen positive subset (MITT-PA/SA) and microbiological per-protocol (MPP) populations, which will be the primary populations for efficacy analysis. Efficacy analyses will also be conducted on the Clinical intent-to-treat (CITT) and per-protocol (PP) populations. Safety summaries will be based on the Safety population. These populations are defined in Section 10.1.4.

#### 10.1.1 Sample Size

Planned enrollment is 500 children, adolescents and adults. Patients will be stratified at enrollment so that approximately 50% of those enrolled will be younger than 18 years old and approximately 50% will be over 18 years old or older. Stratification is being performed to ensure adequate representation of each age group in the study and not for statistical considerations.

We have not been able to find an accurate estimation of study's main variable (therapeutic cure) in previous investigations with Ciprofloxacin 0.3% otic solutions in the treatment of AOE. Rates of patients cured, with different definitions from ours, have been estimated within a range between 60% and 70%. Moreover, in two comparative trials testing the same combination (same product) versus Ciprofloxacin alone in the treatment of AOMT, the percentage of therapeutic cure in patients with *Pseudomonas aeruginosa* and *Staphylococcus aureus* was around 50%.

For the calculation of the sample size for this study, the assumption is made that the Ciprofloxacin alone group will have a therapeutic cure rate of 62%, and that the combination will increase it by a relative 25%, which would represent a therapeutic cure rate of 78%. Assuming a two-sided significance level of 5%, and a statistical power of 80%, the required number of patients in each group would be 150. The randomization schedule is defined as 2:2:1 (Ciprofloxacin plus Fluocinolone acetonide : Ciprofloxacin : Fluocinolone acetonide), so the total number of evaluable patients to be recruited is 375 (150 : 150 : 75).

In this study, evaluable patients are those with a positive pathogen microbiological culture at baseline (MITT population). From previous studies in AOE, the rate of patients included with a negative culture at baseline is approximately 25%, and therefore the number of patients to be finally recruited to obtain 375 evaluable patients would be 500.

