Sample Size calculation:	
We have not been able to find an accurate estimation of study's main variable (therapeutic cure) in previous investigations with Ciprofloxacin 0.3% otic solutions in the treatment of AOE. Rates of patients cured, with different definitions from ours, have been estimated within a range between 60% and 70%. Moreover, in two comparative trials testing the same combination (same product) versus Ciprofloxacin alone in the treatment of AOMT, the percentage of therapeutic cure in patients with Pseudomonas aeruginosa and Staphylococcus aureus was around 50%.
 
For the calculation of the sample size for this study, the assumption is made that the Ciprofloxacin alone group will have a therapeutic cure rate of 62%, and that the combination will increase it by a relative 25%, which would represent a therapeutic cure rate of 78%. Assuming a two-sided significance level of 5%, and a statistical power of 80%, the required number of patients in each group would be 150. The randomization schedule is defined as 2:2:1 (Ciprofloxacin plus Fluocinolone acetonide / Ciprofloxacin / Fluocinolone acetonide), so the total number of evaluable patients to be recruited is 375 (150 : 150 : 75).
 
In this study, evaluable patients are those with a positive microbiological culture at baseline (MITT population). From previous studies in AOE, the rate of patients included with a negative culture at baseline is approximately 25%, and therefore the number of patients to be finally recruited to obtain 375 evaluable patients would be 500.

---------------------------------	---

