### **5.4 Planned Sample Size and Study Sites**

Planned enrollment is 500 children, adolescents and adults. Patients will be randomized in a 2:2:1 ratio (Ciprofloxacin 0.3% plus Fluocinolone acetonide 0.025% otic solution : Ciprofloxacin 0.3% otic solution : Fluocinolone acetonide 0.025% otic solution), with the aim of including 375 evaluable patients.

Patients will be stratified at enrollment so that approximately 50% of those enrolled will be younger than 18 years old and approximately 50% will be 18 years old and older. It is expected that approximately 80% of enrolled patients will complete the study.

About 50 study sites in US will recruit patients. Enrollment will be competitive, i.e., each study site will continue to enroll patients until recruiting the total of 375 evaluable patients. No study site may enroll more than 50 patients.

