#### ***10.1.4 Analysis Populations***

There will be 5 populations defined for this study: Safety, Clinical intent-to-treat (CITT), Microbiological intent-to-treat (MITT), Clinical per-protocol (CPP), and Microbiological per-protocol (MPP).

The **Safety population** will include all patients who received any study medication.

The **CITT population** will include all patients who were randomized.

The **MITT population** will include all CITT patients whose Visit 1 microbiological culture yields 1 or more pathogens, as defined in Section 7.1.2.

The **MITT-PA/SA population** will include the pathogen positive subset of the CITT population which includes all patients who received study medication and had culture positive for *P. aeruginosa* and/or *S. aureus* at baseline in the evaluable ear.

The **CPP population** will include all CITT patients who:

- Satisfied all inclusion and exclusion criteria;
- Did not receive any prohibited concomitant medications;
- Did not have any other major protocol violations;

- Completed Visit 3 and Visit 4 (unless the patient was deemed a clinical failure at an earlier visit than Visit 4); and
- Had compliance rates between 80% and 120% as defined in Section 10.1.8 (patients who are deemed Clinical Failures are to be included if they had compliance rates between 80% and 120% during the first 3 days of study treatment).

The **MPP population** will include all CPP patients whose Visit 1 microbiological culture yields 1 or more pathogens and who had microbiological results (when patient has material to culture) from Visit 3 and/or Visit 4 unless the patient was deemed a clinical failure at an earlier visit than Visit 4.

For the CITT and MITT populations, the treatment group of a patient will be determined by the treatment group to which the patient was randomized.

For the Safety, CPP and MPP populations, the treatment group of a patient will be determined by the treatment the patient received, not necessarily the group to which he or she was randomized. The Safety population will be used for all safety analyses.

The primary populations for efficacy analyses will be the MITT population.

The populations to be used for each of the secondary efficacy endpoints will be detailed in the Statistical Analysis Plan.

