##### ***10.1.10.1 Primary efficacy endpoint***

###### ***Primary analysis of the primary endpoint***

The primary efficacy endpoint will be the therapeutic cure at Visit 3 in the MITT-PA/SA population.

In order for the requirements of the combination policy to be satisfied, both comparisons of the combination to the components alone must show the combination to be statistically significantly better than the component alone using a two-sided 0.05 significance level.

The number and percentage of patients with therapeutic cure at Visit 3 will be summarized by treatment group. The proportion of patients with a therapeutic cure will be compared between the treatment groups by using a chi-squared test.

Efficacy analyses of the primary endpoint will also be conducted on the MITT, MPP, CITT and CPP populations.

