For the Safety, CPP and MPP populations, the treatment group of a patient will be determined by the treatment the patient received, not necessarily the group to which he or she was randomized. If a patient receives only Fluocinolone acetonide for the duration of the study, they will be summarized in the Fluocinolone acetonide treatment group. If a patient receives only Ciprofloxacin for the duration of the study, they will be summarized in the Ciprofloxacin treatment group. Otherwise, patients will be summarized in the Ciprofloxacin plus Fluocinolone acetonide treatment group. The Safety population will be used for all safety analyses.

Unless otherwise noted, all efficacy analyses and summaries will be based on the MITT-PA/SA population, which will be the primary population for efficacy analysis. Efficacy analyses will also be conducted on the CITT, MITT, CPP and MPP populations. Safety summaries will be based on the Safety population.

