4.10 Determination of Sample Size

Planned enrollment is 500 children, adolescents and adults. Patients will be stratified at enrollment so that approximately 50% of those enrolled will be younger than 18 years old and approximately 50% will be over 18 years old or older. Stratification is being performed to ensure adequate representation of each age group in the study and not for statistical considerations.

We have not been able to find an accurate estimation of study's main variable (therapeutic cure) in previous investigations with Ciprofloxacin 0.3% otic solutions in the treatment of AOE. Rates of patients cured, with different definitions from ours, have been estimated within a range between 60% and 70%. Moreover, in two comparative trials testing the same combination (same product) versus Ciprofloxacin alone in the treatment of AOMT, the percentage of therapeutic cure in patients with *Pseudomonas aeruginosa* and *Staphylococcus aureus* was around 50%.

For the calculation of the sample size for this study, the assumption is made that the Ciprofloxacin alone group will have a therapeutic cure rate of 62%, and that the combination will increase it by a relative 25%, which would represent a therapeutic cure rate of 78%. Assuming a two-sided significance level of 5%, and a statistical power of 80%, the required number of patients in each group would be 150. The randomization schedule is defined as 2:2:1 (Ciprofloxacin plus Fluocinolone

acetonide:Ciprofloxacin:Fluocinolone acetonide), so the total number of evaluable patients to be recruited is 375 (150 : 150 : 75). It is expected that approximately 80% of enrolled patients will complete the study.

In this study, evaluable patients are those with a positive pathogen microbiological culture at baseline (MITT population). From previous studies in AOE, the rate of patients included with a negative culture at baseline is approximately 25%, and therefore the number of patients to be finally recruited to obtain 375 evaluable patients would be 500.

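### The sample size and 80% power are set for all pathogen-positive patients (MITT), but the primary test uses only the P. aeruginosa/S. aureus subset (MITT-PA/SA), whose size and power are not stated

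*Protocol*

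**What the plan says.** **Sample size.** Protocol 10.1.1 and SAP 4.10 assume cure rates of 62% on ciprofloxacin and 78% on the combination (a 25% relative increase), two-sided 5% significance and 80% power. This gives 150 per main arm and, at 2:2:1, 375 evaluable patients. The protocol defines evaluable as follows: "In this study, evaluable patients are those with a positive pathogen microbiological culture at baseline (MITT population"). The SAP repeats the sentence. The synopsis drops the word pathogen: "evaluable patients are those with a positive microbiological culture at baseline (MITT population"). The only step from evaluable to enrolled is that "the rate of patients included with a negative culture at baseline is approximately 25" percent, which takes 375 to 500. Protocol 5.4 ties recruitment to the same count: "each study site will continue to enroll patients until recruiting the total of 375 evaluable patients".

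**Primary analysis.** Protocol 10.1.10.1 states: "The primary efficacy endpoint will be the therapeutic cure at Visit 3 in the MITT-PA/SA population". Protocol 7.1.4, the synopsis (Statistical Methods) and SAP 4.7.1 and 4.7.2 agree. SAP 4.4 says that, unless otherwise noted, "all efficacy analyses and summaries will be based on the MITT-PA/SA population".

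**Other statements on the primary population.** Protocol 10.1.4 says: "The primary populations for efficacy analyses will be the MITT population". Protocol 10.1 lists MITT, MITT-PA/SA and MPP together, "which will be the primary populations for efficacy analysis".

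**The concern.** MITT takes any pathogen at baseline. MITT-PA/SA takes only treated patients with P. aeruginosa and/or S. aureus. The plan expects the two to differ: protocol 7.1.2 sets up a non-target pathogen category, SAP 4.3.1 counts the two groups separately, and SAP 4.7.3 tabulates T. otitidis and other species. Yet no step takes n from MITT to MITT-PA/SA.

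Recruitment can therefore reach its target of 375 MITT patients with fewer than 375 in the primary test. The stated 150:150:75 and 80% power describe a population in which the primary test is not run.

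Two things add to this. The protocol names the primary population in three ways. Both comparisons must also be significant, but no fluocinolone cure rate and no power for that comparison are given.

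**Working it through.** **1. Reproduce the plan's figure.** Inputs from protocol 10.1.1: p1 = 0.62; p2 = 0.62 × 1.25 = 0.775, which the plan rounds to 0.78; two-sided alpha 0.05 (z = 1.960); power 80% (z = 0.842).

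n = [1.960·√(2·p̄(1−p̄)) + 0.842·√(p1(1−p1) + p2(1−p2))]² / (p2−p1)², where p̄ is the mean of p1 and p2. With continuity correction, n_cc = (n/4)·[1 + √(1 + 4/(n(p2−p1)))]².

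- p2 = 0.775: n = (1.2732 + 0.5389)²/0.155² = 136.7; n_cc = 149.3, so **150**, the stated figure.
- p2 = 0.78: n = (1.2702 + 0.5371)²/0.16² = 127.6; n_cc = 139.8.

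Then 150 + 150 + 75 = 375 and 375/0.75 = 500. The chain is sound, but it ends at MITT.

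**2. Carry it to the primary population.** Let f be the share of MITT patients who are in MITT-PA/SA. The documents do not give f; the range 0.6 to 0.9 is an assumption. The main-arm size is 150f. The planned test is the uncorrected Pearson chi-squared test (SAP 4.7.2). Its power is computed exactly, by summing binomial probabilities over all tables that the test rejects.

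| f | n per main arm | Power, 62% vs 78% | Power, 62% vs 77.5% |
|---|---|---|---|
| 1.0 | 150 | 86% | 84% |
| 0.9 | 135 | 83% | 80% |
| 0.8 | 120 | 78% | 75% |
| 0.7 | 105 | 72% | 69% |
| 0.6 | 90 | 65% | 62% |

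The smallest n with 80% power is 127 per arm (127/150 = 0.85) for 62% versus 78%, and 136 (136/150 = 0.91) for 62% versus 77.5%. On the continuity-corrected basis that yields 150, there is practically no margin.

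Dropout does not reduce n further, because missing and indeterminate outcomes count as failures (protocol 10.1.3, SAP 4.7.1.1).

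**3. The second comparison.** The fluocinolone cure rate is also not in the documents; 50% and 60% are assumed here. The combination is at 78% and ciprofloxacin at 62%. Joint power is summed over the shared combination arm and counts results in favour of the combination.

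| f | Arm sizes | Versus fluocinolone, 50% / 60% | Both comparisons, 50% / 60% |
|---|---|---|---|
| 1.0 | 150:150:75 | 99% / 80% | 86% / 72% |
| 0.8 | 120:120:60 | 97% / 72% | 76% / 60% |
| 0.6 | 90:90:45 | 91% / 60% | 62% / 45% |

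**The case against.** The strongest reply is that no shortfall has been shown. Every loss depends on an assumed f. Under the planned uncorrected test, 150 per arm gives 84% to 86%, which leaves room down to an f of about 0.85 or 0.91. The documents also call P. aeruginosa and S. aureus the most common causative organisms (protocol 2.1, SAP 1), so f may be high. This stands as far as it goes: a power deficit is possible, not proven. But most common is not a proportion, and the mismatch between the two populations does not depend on f.

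A second reply is loose terminology. The documents describe MITT-PA/SA as the pathogen-positive subset, so a positive pathogen culture in 10.1.1 might mean that group. The explicit MITT label in both sample-size sections, and the separate definitions of the two populations, rule this out as the written meaning.

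Third, the conflict over the primary population is partly settled. The list in protocol 10.1 applies unless otherwise noted, and the SAP is consistent. The flat statement in 10.1.4 still contradicts 7.1.4 and 10.1.10.1.

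Fourth, fluocinolone power is a separate omission, and the 60% case puts an antibiotic-free arm within 2 points of ciprofloxacin. That is fair. At 50%, joint power is within about 3 points of the ciprofloxacin comparison alone. The point is secondary and the main conclusion does not rest on it.

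**Conclusion.** The concern holds. The figures 150, 375 and 500 are computed correctly, but they belong to MITT, while the primary test is in MITT-PA/SA. As written, the plan states neither the size nor the power of its primary analysis, and protocol 10.1.4 names a different primary population.

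How much power is lost cannot be settled from the documents. For an assumed f of 0.9 to 0.6, power against ciprofloxacin is 83% to 65% (62% versus 78%) or 80% to 62% (62% versus 77.5%). It stays at 80% or more if f is at least about 0.85 or 0.91. Confidence is high on the mismatch; the size of any deficit is conditional on f. Because this is the sole primary analysis and the correction is cheap, it should be made.

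**What to change.** Keep 500 enrolled and 375 MITT patients, and make these wording changes:

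1. Label 375 and 150:150:75 as an MITT target in the synopsis, protocol 5.4 and 10.1.1, and SAP 3.1 and 4.10.
2. In protocol 10.1.1 and SAP 4.10, state that the primary analysis is in MITT-PA/SA. Give the assumed proportion f with its source, the expected arm sizes 150f:150f:75f, and the resulting power against ciprofloxacin. For example, f = 0.8 gives 120:120:60, with 78% power (62% versus 78%) or 75% (62% versus 77.5%).
3. State an assumed fluocinolone cure rate, the power of that comparison, and the power for both together.
4. In protocol 10.1 and 10.1.4, name MITT-PA/SA as the primary efficacy population and the others as supportive, as SAP 4.4 already does.
5. As a minor clarification, say whether the 25% negative rate includes cultures that grow only non-pathogens. Protocol 7.1.2 defines negative as no growth, while SAP 4.7.2 treats non-pathogen growth as negative for a pathogen. Use the same pathogen wording in the synopsis as in 10.1.1.

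This needs no extra enrolment and no change to the test. The cost is that the stated power will probably be less favourable. Disclosure does not restore lost power. If the sponsor wants 375 patients in MITT-PA/SA itself, enrolment would be 375/(0.75f): 556 at f = 0.9 or 625 at f = 0.8. The recruitment rule in 5.4 would then have to count that population.
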